### 5 Study Agent/Interventions

#### 5.1 Disposition and Dispensation

Sanofi/Genzyme will supply pre-filled syringes of sarilumab and placebo. Study agent and placebo will be distributed via the NIH pharmacy according to standard pharmacy procedures.

##### 5.1.1 Formulation, Packaging, and Labeling

Each package will be individually labeled in the NIH pharmacy with the patient ID number, dosing instructions, recommended storage conditions, the name and address of the manufacturer, and that the agent should be kept out of reach of children.

#### 5.2 Study Agent Storage and Stability

Syringes of sarilumab should be stored at 2°C-8°C and away from the light. Do not freeze. Syringes may also be stored in their outer carton at room temperature (< 25°C) for up to 14 days. The drug should not be used past the expiration date printed on the carton.

#### 5.3 Randomization and Blinding/Unblinding Procedures

Eligible participants will be allocated 1:1 to study agent or placebo. A randomization scheme will be generated by the study statistician who will provide a randomized list of arm assignments to the NIH CC Pharmacy. A permuted block approach, with varying block sizes, will be used for the randomization process.

The participants, the investigators, and all who are involved in the evaluation of the study participants including study monitors and central laboratory personnel are blinded to a participant's treatment assignment until all participants have completed the week 16 visit. The NIH research pharmacist is identified as the unblinded third party who will be in charge of treatment assignment, maintaining study supplies/inventory list, and preparing the blinded study medication for each participant. The NIH research pharmacist will be independent of any study assessments. To maintain blinding, any discussion of the treatment assignment between the clinicians and the pharmacy staff is prohibited until the study is unblinded. Unblinding will occur when the final participant completes their week 28 visit (section 6.2.5), or in the case of early termination or study drug discontinuation, after the participant's final study visit.

Participants will be assigned a screening number after completion of the protocol consent for enrollment in the study in the Clinical Research Information Management System of the NIAID (CRIMSON). The study statistician will generate the randomization codes. These codes will be maintained by the NIH research pharmacist. A study allocation number (1, 2, etc) will be assigned when the participant is ready to be randomized. Randomization is defined as the time that the pharmacy is notified that this new participant, with this study allocation number, is being enrolled. This should coincide with the day that the first dose of study drug is administered. Randomization will continue until there are 30 participants who initiate study drug and have at least the first post-baseline QoL measurement at 4 weeks. Note that participants who do not meet these criteria still remain in the study, and attempts to obtain subsequent QoL measures should be made.

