#### Figure 1 Study Schedule

## 3.2 Study Endpoints

### 3.2.1 Primary Endpoints

1. QoL at 16 weeks post-initiation of study drug/placebo using the MC-QoL.
2. Frequency and severity of AEs during the randomized double-blinded placebo-controlled treatment period.

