### **5.3.1 Emergency Unblinding**

If a participant experiences an AE whose management (eg, diagnostic procedures, treatment) in the opinion of the principal investigator (PI) or designee would differ depending on the study arm, or in the case of pregnancy, then the PI or designee will contact the NIH CC Pharmacy for release of the randomization code. The sponsor and DSMB executive secretary will be informed within 1 business day of any request for unblinding. The participant will remain enrolled in the study and the data will be used for analysis.

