## **6.2 Randomized, Double-Blinded, Placebo-Controlled Treatment Period**

### **6.2.1 Baseline (Days –2 to 0)**

After eligibility has been confirmed, participants will visit the NIH CC for baseline testing. Participants may be admitted as inpatients and will be randomized to receive sarilumab or placebo. The following procedures will then be done at baseline:

1. Physical exam with vital signs.
2. Overview of medical/medication history.
3. Assessment of baseline symptoms of ISM.

4. Assessment of AEs.
5. Blood draw for clinical evaluations:
  - a. CBC/diff.
  - b. Acute care, hepatic, and mineral panels.
  - c. PT/PTT.
  - d. Total protein.
  - e. Lipid panel.
  - f. Serum tryptase.
  - g. C-reactive protein (CRP).
6. Urine or serum pregnancy test (for participants of childbearing potential only).
7. Blood draw for DNA and RNA collection.
8. Collection of serum (8 mL serum separator tube [SST]) for storage.
9. Serum IL-6 levels.
10. Serum markers of bone marrow resorption and deposition.
11. Plasma for storage (10 mL green top tube [GTT]).
12. Whole blood for storage (3 mL lavender top tube [LTT]).
13. MC-QoL.
14. SCORMA.
15. MSAS.
16. MQLQ/MSAF.
17. *KIT* D816V mutation analysis on blood.
18. Flow cytometry on blood.
19. Photography of affected areas (optional).
20. Skin punch biopsy (optional).

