#### **6.2.5 Post-treatment Visit (Week 28 ± 7 days)**

The participant will return to the NIH CC for a post-treatment visit 12 weeks (± 7 days) after the peak treatment follow-up visit (section 6.2.4). The participant will undergo the following procedures:

1. Physical exam with vital signs.
2. Overview of medical/medication history.
3. Assessment of AEs.
4. Blood draw for clinical evaluations:
  - a. CBC/diff.
  - b. Acute care, hepatic, and mineral panels.
  - c. PT/PTT.
  - d. Total protein.
  - e. Lipid panel.
  - f. Serum tryptase.
  - g. CRP.
5. Pregnancy test (serum or urine, for participants of childbearing potential only).
6. Collection of serum (8 mL SST) for storage.
7. Serum IL-6 levels.
8. Serum markers of bone marrow resorption and deposition.
9. Plasma for storage (10 mL GTT).
10. Whole blood for storage (3 mL LTT).
11. MC-QoL.
12. SCORMA.
13. MSAS.

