14. MQLQ/MSAF
15. KIT D816V mutation analysis on blood.
16. Flow cytometry on blood.
17. Photography of affected areas.
18. Diary review.

At the end of this visit, participants who continue to meet all eligibility criteria (sections 4.2 and 4.3) will be offered the opportunity to continue on sarilumab for another 52 weeks. Prior to beginning the open-label treatment, a safety assessment of any AEs that may have occurred during the randomized treatment period will be reviewed with the participant. Participants who decline will end their participation after this visit. Those who accept will continue on the study as described below (section 6.3).

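### Section 5.3 gives two ends of the blind, the last week-16 visit and the last week-28 visit, and its early-termination clause does not say whether individual codes open sooner

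*Combined protocol and SAP*

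**What the plan says.** Section 5.3 deals with the end of the blind twice in one paragraph.

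- Participants, investigators and everyone who evaluates participants are blinded "until all participants have completed the week 16 visit".
- A few sentences later: "Unblinding will occur when the final participant completes their week 28 visit". An alternative follows, "in the case of early termination or study drug discontinuation", which is tied to the participant's final study visit.
- In between, clinicians and pharmacy staff may not discuss assignments until the study is unblinded. No date is attached to that.

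Individual code release has its own rule in section 5.3.1. If management of an AE would depend on the arm, or in pregnancy, "then the PI or designee will contact the NIH CC Pharmacy for release of the randomization code". Section 12.4.4 also requires unblinding in pregnancy.

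The second primary endpoint (section 3.2.1) is "Frequency and severity of AEs during the randomized double-blinded placebo-controlled treatment period". Section 6.2 is headed "Randomized, Double-Blinded, Placebo-Controlled Treatment Period" and contains the week-28 visit as section 6.2.5: "The participant will return to the NIH CC for a post-treatment visit 12 weeks" (±7 days) after the week-16 visit. Appendix B also lists week 28 in its double-blinded column group. The Protocol Summary, on the other hand, calls these 12 weeks a washout.

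**The concern.** Two things are unsettled.

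**The study-wide date.** If staff act on the week-16 sentence, anyone who has not yet reached week 28 is followed open from then on. AE severity is graded by the investigator (section 12.3.1), who also judges causality (section 12.3.2), and the week-28 MC-QoL is self-reported. Knowledge of the arm can influence all of these. On the section headings, AEs between weeks 16 and 28 count towards a primary endpoint.

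**The early-termination clause.** It does not say whose code is opened, to whom, or whether this can happen before the study-wide date. If it works person by person, staff could learn individual assignments without an emergency while others are still being randomised in permuted blocks and assessed.

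There is also a practical consequence. Section 12.9.3 requires any intentional or unintentional unblinding to be reported to the DSMB within 1 business day. With two end dates and an unclear clause, staff cannot tell a planned release from a reportable event.

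**Working it through.** The plan states no figure on this point. Its one design figure, power above 90% (section 15.2), was reproduced by simulating the stated recipe: 99.8% in 20,000 replicates. It does not depend on when the blind ends.

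**1. Can the texts be reconciled?** The week-16 sentence says how long people are blinded but names no release event. The week-28 sentence names one. Sections 5.3.1 and 12.4.4 cover only emergencies and pregnancy. So week 28 may be the intended trigger, but no section says so.

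**2. Does week 28 lie inside the double-blinded period?** By the section 6.2 heading and Appendix B, yes. The AE review at the end of the week-28 visit ("a safety assessment of any AEs that may have occurred during the randomized treatment period will be reviewed with the participant") is weaker support, because it would fit an earlier end as well.

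**3. How many participants would be open?**

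Inputs:
- 30 participants and 5-year accrual (Protocol Summary).
- A gap of 12 weeks = 84 ÷ 30.44 days = 2.76 months (section 6.2.5).
- Uniform entry over the accrual period *T* in months (assumption).
- Two alternatives for *T*. The stated study dates, October 2018 to July 2027, span 105 months; less up to 91 weeks on study (about 21 months), they leave room for about 84 months of accrual. A faster accrual of 36 months is assumed.

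At the last participant's week-16 visit, the number between weeks 16 and 28 is 1 + (29 ÷ *T*) × 2.76. The last participant has 12 weeks still to run and the others 6 on average, so the open participant-weeks are 12 + 6 × (29 ÷ *T*) × 2.76. The denominators are 30 × 28 = 840 participant-weeks (weeks 0 to 28) and 30 × 12 = 360 (weeks 16 to 28).

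| Accrual | Participants | Participant-weeks open | Of 840 | Of 360 |
|---|---|---|---|---|
| 84 months | 1 + 0.95 = 1.95 | 12 + 5.7 = 17.7 | 2.1% | 4.9% |
| 60 months (stated) | 1 + 1.33 = 2.33 | 12 + 8.0 = 20.0 | 2.4% | 5.6% |
| 36 months (assumed) | 1 + 2.22 = 3.22 | 12 + 13.3 = 25.3 | 3.0% | 7.0% |

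The ±7-day window changes little: at 60 months, an 11-week gap (2.53 months) gives 2.22 participants and a 13-week gap (2.99 months) gives 2.45. The 840 denominator fits the premise that the AE endpoint runs to week 28; the 360 describes the follow-up segment alone.

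**4. How many individual codes might the early-termination clause open?** The documents give no discontinuation rate for this population, so no number is offered.

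**The case against.** The best defence is that the two sentences do different jobs: week 16 is a minimum and week 28 the trigger. The week-16 sentence authorises no release, and the ban on discussion with the pharmacy runs until the study is unblinded. This is a fair reading and may be what was meant. It does not remove the conflict, because the first sentence as written ends the blind 12 weeks sooner.

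A reader might infer that the primary efficacy result is exposed. The documents do not support that. Both study-wide dates require every participant to have completed week 16, so under either one the week-16 MC-QoL is collected blind. Any risk to it would come indirectly, through codes opened early under the other clause.

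It can also be said that the AE endpoint stops at week 16: the last dose is at week 14, the week-28 visit is titled post-treatment, and the summary speaks of a washout. This stands as a limit. If it is right, only week-28 data are affected. The AE analysis is descriptive in any case (sections 15.3 and 15.5).

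A reader might further infer that the plan does open each early terminator's code. The text does not establish this. The participant in that clause may be the final participant, which makes it a fallback trigger. It may be each person who stops, which is how section 6.2.6 uses early termination. The final study visit may even mean the week-55 visit, which carries that title in section 6.3.2. Varying block sizes also reduce what one opened code reveals, though they do not remove it. A worry about replacement decisions is speculative, since section 12.8.1 keeps all randomised participants in the analysis.

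**Conclusion.** The conflict between week 16 and week 28 is real, stands in current text and should be corrected; confidence in this is high. Its effect is small. Under uniform entry of 30 participants, following the week-16 sentence would leave about 2.0 to 3.2 participants open, for about 18 to 25 participant-weeks: 2.1 to 3.0% of weeks 0 to 28, or 4.9 to 7.0% of weeks 16 to 28. What is at stake is the last participants' AEs after week 16, if the endpoint runs to week 28, and their week-28 questionnaires.

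The early-termination clause is a genuine ambiguity, but its harm depends on the reading and cannot be sized from the documents. The finding does not show that the trial is unblinded early or that its efficacy result is compromised.

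**What to change.** In section 5.3:

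- Change week 16 to week 28 in the blinding sentence. State one rule: codes stay closed to participants, investigators and evaluators until every randomised participant has completed week 28 or has left the randomised period, with section 5.3.1 and the pregnancy provision in section 12.4.4 as the only exceptions.
- Reword the early-termination clause so that it sets only this general trigger and opens no individual code to investigators or evaluators earlier.

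The change is to protocol wording only and adopts the plan's own week-28 trigger. It has two costs. General unblinding comes about 12 weeks (11 to 13 with the visit window) after the last week-16 visit. And if the clause was meant to let people learn their arm after their own last visit, early terminators lose that: someone who stops early may wait for the rest of accrual, possibly years. The sponsor should accept that trade-off knowingly.

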### **5.3.1 Emergency Unblinding**

If a participant experiences an AE whose management (eg, diagnostic procedures, treatment) in the opinion of the principal investigator (PI) or designee would differ depending on the study arm, or in the case of pregnancy, then the PI or designee will contact the NIH CC Pharmacy for release of the randomization code. The sponsor and DSMB executive secretary will be informed within 1 business day of any request for unblinding. The participant will remain enrolled in the study and the data will be used for analysis.

## **5.4 Preparation, Administration, and Dosage of Sarilumab and Placebo**

Sarilumab is supplied in single-use pre-filled syringes (150 or 200 mg/1.14 mL) for SC injection. Placebo will be supplied by Sanofi/Genzyme in the same fashion in pre-filled syringes. The volume of the placebo dose is also 1.14 mL.

The pausing criteria are described in section 12.6. Participants who resume after a pause as a result of lab abnormalities may have their dose temporarily reduced from 200 to 150 mg, at the discretion of the PI (in consultation with the CSO), until these values return to stated thresholds (section 12.6.2), per the sarilumab package insert.

## 5.5 Study Product Accountability Procedures

The NIH pharmacy will maintain accurate drug accountability records. A binder containing instructions and the required accountability documentation will be provided to the study pharmacist. When the study is completed, the accountability documentation will be maintained at the NIH CC per standard procedures. All unused study drug must be disposed of upon authorization by NIAID or its designee. All records regarding the disposition of study drug must be available for inspection by the study monitors and regulatory authorities.

## 5.6 Concomitant Medications and Procedures

All concomitant prescription and nonprescription (including over-the-counter) medications taken during study participation will be recorded. Reduction in medication use will be noted and documented based on clinic intake and participants will be required to maintain a medication change diary ([Appendix H](#)) for monitoring of medications. For this protocol, a prescription medication is defined as a medication that can be prescribed only by a properly authorized/licensed clinician.

Various in vitro and limited in vivo human studies have shown that cytokines and cytokine modulators can influence the expression and activity of specific cytochrome P450 (CYP) enzymes and therefore have the potential to alter the pharmacokinetics of concomitantly administered drugs that are substrate of these enzymes. Liver CYPs are downregulated by IL-6, so inhibition of IL-6 may restore liver CYP activity. Drug doses therefore may need to be modified in light of increased CYP-mediated metabolism, especially in drugs with a narrow therapeutic index. The effect of sarilumab on CYPs can persist for weeks after sarilumab therapy ends. Therefore, drugs with a narrow therapeutic that are CYP metabolized will be identified and monitored for clinical effects and blood levels if necessary.

## 5.7 Prohibited Medications and Procedures

Participants may not receive any live vaccine while they are being treated with sarilumab because inhibition of IL-6 may obstruct the normal immune response.

## 6 Study Schedule

All visits will take place at the NIH CC. Study participation will include an optional inpatient stay for approximately 3 days (baseline testing, randomization, and first dose administration), two full clinic days (screening and peak treatment, which both include a bone marrow examination), 4 half clinic days (doses 3, 5, 7, final study visit), and 4 short clinic visits (doses 2, 4, 6, 8) for AE assessment and injection only. For subjects opting to self administer study agent at home at doses 4, 6, and 8, a visit to NIH will not take place. No history, physical exam, AE collection, pregnancy test or diary review will take place for these subjects. A table of the study

schedule and procedures/evaluations is provided in [Appendix A](#). A table of blood volumes to be collected at each visit is provided in [Appendix B](#).

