### **6.2.3 Doses 2-8 (weeks 2, 4, 6, 8, 10, 12, 14 ± 4 days)**

Participants will return to the NIH CC once every 2 weeks ( $\pm$  4 days) to receive their next dose of study drug or placebo. The exception will be subjects at doses 4, 6, and 8 who have not experienced reactions to the agent. These subjects may opt to self-administer the study agent at home. At each visit where agent will be administered at NIH, before dose administration, the

participant will undergo a physical exam with vital signs, overview of medical history, diary review, and assessment of AEs. At each visits where participants of childbearing potential receive study agent at NIH, they will also have a urine or serum pregnancy test, which must be negative before administration of the study drug. In addition, at the visits for doses 3, 5, and 7 (weeks 4, 8, and 12), participants will undergo the following procedures before dose administration:

1. Blood draw for clinical evaluations:
  - a. CBC/diff.
  - b. Acute care, hepatic, and mineral panels.
  - c. PT/PTT.
  - d. Total protein.
  - e. Lipid panel.
  - f. Serum tryptase.
  - g. CRP.
2. Collection of serum (8 mL SST) for storage.
3. Serum IL-6 levels.
4. Plasma for storage (10 mL GTT).
5. Whole blood for storage (3 mL LTT).
6. MC-QoL.
7. SCORMA.
8. MSAS.
9. MQLQ/MSAF.
10. Photography of affected areas (optional).

As at the first dose visit, participants will be monitored during their injection and for 1 hour after the injection to observe for any immediate drug-related AEs and hypersensitivity reactions. Hypersensitivity reactions will be treated as clinically appropriate.

Participants who have not experienced reactions to the injection after the second dose may, at the request of the participant and the discretion of the PI, be trained to self-inject the study drug/placebo for the fourth, sixth, and eighth doses (weeks 6, 10, and 14). There is no known increase in risks for self injection. Subjects will be provided with dosing materials to take home and instructions for storage and administration. These participants will not have study visits (including pregnancy test, AE evaluation, study diary review or history and physical exam at the NIH for these doses. When a dose is to be self-injected at home, study staff will contact subject to ensure administration took place, and document this in the NIH medical record.

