## 12.2 Documenting, Recording, and Reporting Adverse Events

All AEs occurring from the baseline visit through the final study visit will be documented, recorded, and reported.

At each contact with the participant, information regarding AEs will be elicited by appropriate questioning and examinations and will be:

- immediately documented in the participant's medical record/source document,
- recorded in CRIMSON, and
- reported as outlined below (eg, IND sponsor, IRB, and FDA).

If a diagnosis is clinically evident (or subsequently determined), the diagnosis rather than the individual signs and symptoms or lab abnormalities will be recorded as the AE.

A laboratory abnormality will not be reported as an AE if ALL of the following criteria are met:

- It is no more than "Grade 1" or "Mild" per the protocol-specified toxicity table (or investigator assessment if not listed on the table); AND
- It does NOT require an intervention (eg, discontinuation of treatment, dose reduction/delay, additional assessments, or treatment); AND
- It is assessed by the PI as NOT related to the study agent(s); AND
- It is assessed by the PI as NOT clinically significant (eg, the abnormal value does NOT suggest a disease or organ toxicity).

All abnormal laboratory findings will be reviewed on a routine basis by the PI to identify potential safety signals. An abnormal lab not included on the toxicity table should be assessed in a similar fashion to the criteria above.

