AE = adverse event; HBV = hepatitis B virus; HCV = hepatitis C virus; IL = interleukin; ISM = indolent systemic mastocytosis; MC-QoL = Mastocytosis Quality of Life Questionnaire; MSAS = Memorial Symptom Assessment Scale; Q2W = once every 2 weeks; SCORMA = scoring of mastocytosis index; X = to be performed.

A Participants may be admitted as inpatients for this study visit. Procedures will be performed just once during this period.

B At the discretion of the study team, instead of coming to the NIH for study visits on weeks 6, 10 and 14, participants can self-administer study drug at home. No other procedures will be done at these time points for participants who self-administer.

C This visit will take 1-2 days as outpatients.

D Informed consent will be obtained before any study procedures are conducted on this protocol.

E Patients will be randomized to receive sarilumab or placebo.

F The screening physical exam will include measurement of vital signs, height, and weight.

G Sarilumab/placebo will be administered after the other study procedures have been completed.

H Will be done at screening only if not done within the last 150 days on protocol 02-I-0277 or this protocol.

I Only blood will be collected for *KIT* mutation analysis and flow cytometry at these visits.

j Optional at these visits.

k At visits 4, 6, 8, subjects may self inject at home. At these self administered injection timepoints, no assessments will occur.

	Open Administration Visits					Final Study Visit	Early Termination Visit
	Week 1 a	Week 7 ± 7 days	Week 19 ± 14 days	Week 31 ± 14 days	Week 43 ± 14 days	Week 55 ± 14 days	
Procedures/Evaluations							
Physical exam		X	X	X	X	X	X
Medical/medication history		X	X	X	X	X	X
AE assessment		X	X	X	X	X	X
CBC/diff		X	X	X	X	X	X
Acute care, hepatic, and mineral panels		X	X	X	X	X	X
Lipid panel		X		X			
Pregnancy test (serum or urine)		X	X	X	X	X	X
Serum tryptase		X	X	X	X	X	X
Diary review		X	X	X	X	X	X
Memory aid review		X	X	X	X	X	X
Study drug administration b	X	X	X	X	X		

AE = adverse event; CBC = complete blood count.  
 a Week 1 of the open administration portion of this study immediately follows the post-treatment visit.  
 b Study drug will be administered after all other procedures have been completed.

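### Section 12.2 requires adverse events to be asked about at every contact, but the schedule rules this out at home doses 4, 6 and 8, where a staff contact is mandatory

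*Combined protocol and SAP*

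**What the plan says.** Section 12.2 sets the general rule: "At each contact with the participant, information regarding AEs will be elicited by appropriate questioning and examinations". It covers the baseline visit through the final study visit and makes no exception for doses given at home.

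Section 6.2.3 lets participants without a reaction to the agent self-inject doses 4, 6 and 8 (weeks 6, 10 and 14), at their request and the PI's discretion. For each such dose "study staff will contact subject to ensure administration took place", and this is documented in the medical record. The same section says: "These participants will not have study visits (including pregnancy test, AE evaluation, study diary review", wording that it ties to the visit at the NIH.

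Section 6 gives the purpose of the visits being replaced as "4 short clinic visits (doses 2, 4, 6, 8) for AE assessment and injection only". For home dosing it then says: "No history, physical exam, AE collection, pregnancy test or diary review will take place for these subjects". Appendix A agrees with section 6. Footnote k says "At these self administered injection timepoints, no assessments will occur" and footnote b says "No other procedures will be done at these time points for participants who self-administer". The Protocol Summary likewise describes home doses 4, 6 and 8 as given without study assessments.

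**The concern.** A contact takes place at every home dose, so section 12.2 applies to it, while section 6 and Appendix A say that no AE information is collected then. Staff who ask depart from section 6; staff who do not ask depart from section 12.2. Different staff may resolve this differently, so AE questioning could vary between participants for no planned reason.

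AE frequency and severity during the blinded period is primary endpoint 2 (section 3.2.1). By section 6's own description, AE assessment is one of only two purposes of the short visits. Home dosing removes that purpose, and the contact that replaces the visit is limited to confirming the injection. The risk is late or incomplete recording of short, mild symptomatic events.

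**Working it through.** The plan states no figure on this point, so the check is a comparison of texts and a count from the Appendix A schedule.

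**Do the texts conflict?**

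- Contact at each home dose: required (section 6.2.3).
- AE questions at each contact: required (section 12.2).
- AE collection at home doses: excluded by name in section 6. Footnote k excludes all assessments, and AE assessment is a row of the Appendix A table, so it is covered. Footnote b and the Summary exclude it through broader words.
- Section 6.2.3 also drops the AE evaluation, but as part of the cancelled NIH visit, so it conflicts less directly.

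**Scheduled AE-questioning occasions if the exclusion is followed** (AE row of Appendix A)

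- All doses in clinic, weeks 2 to 16: weeks 2, 4, 6, 8, 10, 12, 14, 16 = 8.
- All three optional doses at home: weeks 2, 4, 8, 12, 16 = 5. Reduction: 1 − 5/8 = 37.5%.
- Two home doses: 6. One home dose: 7.
- Adding Day 0: 9 versus 6; 1 − 6/9 = 33%.
- Day 0 to week 28: 10 versus 7; 1 − 7/10 = 30%.

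**Interval between occasions, from week 4**

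- Nominal: 4 weeks (home) versus 2 weeks (clinic).
- Longest between dosing visits, with ±4-day windows around the nominal week: 28 + 4 + 4 = 36 days versus 14 + 4 + 4 = 22 days.
- Longest before week 16 (±7 days around the nominal week): 28 + 4 + 7 = 39 days versus 14 + 4 + 7 = 25 days.
- Section 6.2.4 can also be read as timing the week 16 visit from the eighth dose. The clinic figure is then 14 + 7 = 21 days, and the home figure can reach (14 + 4 + 4) + 21 = 43 days.

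**Laboratory testing.** Section 6.2.3 schedules bloods as follows: "at the visits for doses 3, 5, and 7 (weeks 4, 8, and 12), participants will undergo the following procedures before dose administration". With week 16 added, blood counts and hepatic panels fall at weeks 4, 8, 12 and 16: 4 versus 4, no difference.

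**Ceiling for the planned 30 participants.** At full home uptake, 3 × 30 = 90 of 8 × 30 = 240 scheduled occasions are lost; at half uptake, 45. The documents do not give the uptake.

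**The case against.** The strongest reply is that the exclusions only list procedures of a visit that no longer happens. In section 6 the list directly follows the statement that there is no visit to the NIH, and section 12.2 speaks of examinations as well as questions, which suits a clinical encounter better than a check that a dose was given. Alternatively, the specific home-dose text could be taken to override the general rule. The first reading is fair for section 6.2.3. It does not settle section 6, whose sentence carries no such limit, or the footnotes, which speak of timepoints rather than visits. Nothing in the plan says that the specific text prevails.

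It is also true that the figure of 5 presupposes that the exclusion is followed; if section 12.2 governs the contact, the count is already 8. Fewer occasions for asking is not the same as fewer events captured. Section 12.2 still requires all AEs to be recorded. The dated, graded diary covers injection-site symptoms, hives, cold symptoms and other events, and is reviewed at the next clinic visit. Home dosing is restricted to participants who have not reacted. These points stand and keep the consequence modest. The diary is not a full substitute, because the participant has to start each entry and its review is among the items dropped at home doses.

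Finally, keeping the exclusion could be a deliberate choice by the sponsor. In that case the plan should say so in section 12.2, which it does not.

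**Conclusion.** The concern holds. Sections 12.2 and 6.2.3 together require AE questioning at each home-dose contact, and section 6 and Appendix A exclude it; the passages must be reconciled. Followed as written, section 6 leaves 5 scheduled questioning occasions instead of 8 between weeks 2 and 16 for a participant with all three doses at home. That is the largest case, and it assumes that nobody asks at the contact.

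The consequence for the trial is limited. Laboratory surveillance is identical, AEs are still assessed at weeks 8, 12 and 16, and section 15.5 plans only a descriptive AE analysis. The documents give no basis for estimating how many events would be missed or whether the arms would differ, and no between-arm bias is claimed. The change is worth making because it concerns a primary endpoint and participant safety, and the contact already exists.

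A separate, smaller inconsistency should be tidied at the same time: section 6 limits the short visits to AE assessment and injection, whereas section 6.2.3 and Appendix A also schedule a physical exam, history, diary review and, where applicable, a pregnancy test at them.

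**What to change.** Amend section 6, section 6.2.3, Appendix A footnotes b and k, and the Protocol Summary sentence. They should state that at the home-dose contact staff ask the standard AE questions, go through the diary with the participant, and record the answers under section 12.2. This brings the count back from 5 to 8. Writing a home-dose exception into section 12.2 would also remove the contradiction, but would leave the count at 5. No dosing, pausing or timing rule needs to change.

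The cost is a few minutes at no more than 3 contacts per participant, or 90 contacts for 30 participants. At an assumed 5 minutes each, 90 × 5/60 = 7.5 staff hours in total; at 3 minutes 4.5 hours, at 10 minutes 15 hours. Section 6.2.3 does not state how or when the contact is made. The estimate assumes a conversation, which fits section 17.1, where data collection by telephone is already foreseen; the amendment should say so. No extra visit or contact is needed.
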